12.5 Other Safety Variables

12.5.1 Columbia-Suicide Severity Rating Scale (C-SSRS)

The C-SSRS is a semi-structured interview that captures the occurrence, severity, and frequency of suicide-related thoughts and behaviors during the assessment period. The interview includes definitions and suggested questions to solicit the type of information needed to determine if a suicide-related thought or behavior occurred.

The C-SSRS contains two required items pertaining to suicidal ideation, four required items pertaining to suicidal behavior, and one required item pertaining to non-suicidal self-injurious behavior. There are eight additional suicidal ideation items and two additional suicidal behavior items which are completed in cases of positive responses for other items, as well as two items for suicide and suicide behavior present during the interview. Most items are rated on a dichotomous scale (yes or no) or 3- or 5-point Likert scale. In addition, the total number of attempts (including interrupted and aborted attempts) is recorded. In the event of a positive categorical response the interviewer can provide text or narrative that further describes the thought or behavior.

Two versions of the C-SSRS are used in this study:

- The "Baseline" version will be administered at the Screening Visit (Visit 1) and will be completed for all subjects.
- The "Since Last Visit" version will be completed for all subjects at all study visits after the Screening Visit (Visit 1).

Listings of the C-SSRS data will be provided for subjects with a positive response.

12.5.2 Post Sleep Questionnaire (PSQ)

The PSQ is a 7-item questionnaire typically used to assess sleep quality with pharmacologic treatment. The questionnaire collects data on average time to sleep, sleep latency, frequency of interrupted sleep, duration of interrupted sleep, total sleep time and sleep quality over the last week. The PSQ will be completed by the parent/LAR with the subject and the responses will be reviewed by the clinician during the study visit. The PSQ will be completed at Baseline (Visit 2), and each visit through Visit 6/ET.

The PSQ results will be summarized by treatment and visit. Continuous variables, for example, time to go to sleep and time spent awake, will be summarized using number of subjects, mean and standard deviation, median, and minimum and maximum values. Categorical values, for example, quality of sleep, will be summarized using number of subjects and percentages for each category.

All PSQ data will be listed for the Safety Set.

12.5.3 Children's Sleep Habit Questionnaire (CSHQ)

The Child's Sleep Habits Questionnaire (CHSQ) consists of 33 items for scoring and several extra items intended to provide administrators with other potentially useful information about respondents. The instrument evaluates the child's sleep based on behavior within 8 different subscales: bedtime resistance, sleep-onset delay, sleep duration, sleep anxiety, night wakings, parasomnias, sleep-disordered breathing, and daytime sleepiness.

- 1. Bedtime resistance (sum of the responses for Goes to bed at same time, Falls asleep in own bed, Falls asleep in other's bed, Needs parent in room to sleep, Struggles at bedtime and Afraid of sleeping alone)
- 2. Sleep-onset delay (Falls asleep in 20 minutes item)
- 3. Sleep duration (sum of the responses for Sleeps too little, Sleeps the right amount and Sleeps same amount each day)
- 4. Sleep anxiety (sum of the responses for Needs parent in room to sleep, Afraid of sleeping in the dark, Afraid of sleeping alone and Trouble sleeping away)
- 5. Night wakings (sum of the responses for Moves to other's bed in night, Awakes once during night and Awakes more than once)
- 6. Parasomnias (sum of the responses for Wets the bed at night, Talks during sleep, Restless and moves a lot, Sleepwalks, Grinds teeth during sleep, Awakens screaming, sweating and Alarmed by scary dream)
- 7. Sleep-disordered breathing (sum of the responses for Snores loudly, Stops breathing and Snorts and gasps)
- 8. Daytime sleepiness (sum of the responses for Wakes by himself, Wakes up in negative mood, Others wake child, Hard time getting out of bed, Takes long time to be alert, Seems tired, Watching TV and Riding in car)

Total sleep disturbance score is sum of the 8 subscale scores minus Needs parent in room to sleep and Afraid of sleeping alone (as Needs parent in room to sleep and Afraid of sleeping alone are included in two subscales (1 and 4) and need to be included once).

Total sleep disturbance score, each subscale score and each individual item will be summarized using descriptive statistics (n, mean, SD, minimum, median, and maximum) at each visit (and Visit 6/ET) by treatment group. All CSHQ data will be listed for the Safety Set.

12.6 Exploratory Safety Endpoints

Safety data for TEAEs, vital signs, ECGs, clinical laboratory test results, PSQ, and CSHQ will be descriptively summarized by treatment within each age group (6-8 years and 9-12 years). TEAEs will also be descriptively summarized for overall AEs, AEs by SOC and PT, frequently occurring AEs within each sex group (male and female), race group (white and non-white), and ethnic group.

13. CLINICAL PHARMACOKINETIC AND PHARMACODYNAMIC ANALYSES

Pharmacokinetic and pharmacodynamics data will not be collected for this study.

14. OTHER ANALYSES

No other analyses are planned for this study.

15. INTERIM ANALYSIS

In order to maintain sufficient study power to detect a clinically meaningful treatment effect for the primary efficacy endpoint, a blinded interim analysis at the late stage of the trial (when approximately 75% of all randomized subjects have either completed or discontinued from the study) will be performed to reassess the sample size in case of an underestimated variability postulated at the design stage.

Using the cumulative real data, a blinded, pooled analysis of both treatment groups for estimating variability will be conducted. If the re-estimated pooled standard deviation is larger than the 14 postulated at the design stage, the final total number of subjects to be enrolled will be calculated using the re-estimated pooled standard deviation together with the assumed treatment difference of 11.9 (Friede et al, 2006). If the re-estimated pooled standard deviation is smaller than 14, the sample size will not be adjusted. Using the pooled common variance estimated to do a blinded sample size re-estimation does not inflate the Type I error. The details for estimating the pooled SD are included in Appendix 1.

16. DATA MONITORING/REVIEW COMMITTEE

An external independent Data Monitoring Committee (DMC) was set up to review the data pertaining to safety and tolerability of the study therapy for the duration of this program, which includes studies SHP465-112, SHP465-308, and SHP465-309. The DMC will review the data pertaining to safety and tolerability of the study therapy. Active surveillance for insomnia and decreased appetite leading to weight loss are included. Confidentiality of the unblinded DMC analyses is a critical concern and to address this, an unblinded independent reporting team will be identified within a CRO. The independent reporting team will have no involvement in the conduct of the study. Further details regarding the DMC can be found in the DMC charter, which will be available before the administration of investigational product.

17. COMPUTER METHODS

Statistical analyses will be performed using Version 9.3 (or newer) of SAS^{\circledast} on a suitably qualified environment.

18. CHANGES TO ANALYSES SPECIFIED IN PROTOCOL

18.1 Handling of the Unintentional Urine Drug Screen

At the end of this study, after completing the final on-treatment efficacy and safety assessments, urine drug screens were erroneously performed for one subject at last visit (Visit 6) and 9 subjects who were rolled over to the long-term safety extension study (SHP465-308). Thus, the site and vendor personnel might have been unblinded to treatment drug information of these subjects although a quick action was taken to remove and restrict access to the urine drug screen results. To assess any compromise to data integrity following the potential unblinding for the ten (10) subjects, Shire and PPD study teams performed a thorough investigation of data collected for study primary efficacy, secondary efficacy and safety analyses, including eCOA data collected on the ERT devices and data entered into the EDC.

This investigation showed no patterns of data changes or data integrity concerns which would be indicative of actions based on unblinded information. It was concluded that there was no evidence of the introduction of bias that would affect the aggregate data reported. In addition, Shire respects the value for each subject participant in the study, therefore decided to include all subjects in the final study analysis.

As a conservative measure to evaluate whether the potential unblinding modified the efficacy results due to the unintentional urine drug screen, sensitivity analyses of the primary efficacy (ADHD-RS-5 total score) and key secondary efficacy (CGI-I) analyses will be performed, in which these 10 subjects were excluded from the FAS (see Section 11.5).

19. DATA HANDLING CONVENTIONS

19.1 General Data Reporting Conventions

Continuous variables will be summarized using the following descriptive statistics: n, mean, median, SD, minimum, and maximum. Unless specified otherwise, summary statistics will be presented to 1 more significant digit than the raw data. The minimum and maximum values will be presented to the same number of decimal places as the raw data; the mean and median will be presented to 1 more decimal place than the raw data; and the SD and standard error will be presented to 2 more decimal places than the raw data.

Categorical and count variables will be summarized by the number of subjects (n) and the percent of subjects in each category. Percentages will be presented to 1 decimal place.

P-values will generally be presented to 4 decimal places; values less than 0.001 will be presented as <0.001.

19.2 Derived Efficacy Endpoints

The ADHD-RS-5 total score will be calculated as the sum of the individual items from the ADHD-RS-5. The ADHD-RS-5 is an 18-item questionnaire that requires the respondent to rate the frequency of occurrence of ADHD symptoms as defined by Diagnostic and Statistical Manual of Mental Disorders criteria. Each item is scored on a 4-point scale ranging from 0 (never or rarely) to 3 (very often) with total scores ranging from 0 to 54. As specified in Section 11.1, the 18 items will also be grouped into 2 subscales: hyperactivity/impulsivity (9 items for hyperactivity/impulsivity) and inattentiveness (9 items for inattentiveness), with subscale scores ranging from 0-27.

A missing individual item in the ADHD-RS-5 is imputed as follows (DuPaul et al., 2016): if only 1 single item is missing in a given subscale, the mean score for all other items in the subscale for the specific visit is imputed as the score rounded up to the nearest integer for the missing score. The total score is computed as the sum of the imputed subscale scores. If more than 1 item is missing in a subscale then the subscale score and total score would be missing.

19.3 Association of Early Termination Assessments to Scheduled Visits

For purposes of reporting early termination assessments during the study, each early termination visit will be assigned the next nominal visit number after the last completed visit. This rule applies to both efficacy variables (e.g., ADHD-RS-5 total score) and safety variables (e.g., vital signs) that are analyzed and/or summarized by visit.

19.4 Repeated or Unscheduled Assessments of Safety Parameters

If a subject has repeated assessments before the start of double-blind investigational product, then the results from the final assessment made prior to the start of double-blind investigational product will be used as baseline.

Protocol SHP465-309

If a subject has repeated assessments at any post-baseline visit, the first recorded assessment will be assigned to the visit for generating descriptive statistics. For vital signs (sitting systolic and diastolic blood pressure, and pulse), this will be the average of the 3 measurements from the first recorded assessment.

If final on-treatment safety assessments are repeated or unscheduled, the last post-baseline assessment will be used as the final on-treatment assessment for generating descriptive statistics. For vital signs (sitting systolic and diastolic blood pressure, and pulse), this will be the average of the 3 measurements from the last post-baseline assessment.

However, all post-baseline assessments will be used for PCI value determination and all assessments will be presented in the data listings.

All repeat and unscheduled visits will be listed.

19.5 Missing Dispensed or Returned Date or Number of Capsules of Investigational Product

When the date of the last dose of double-blind investigational product is missing for a subject in the Safety Set, all efforts should be made to obtain the date from the investigator. If it is still missing after all efforts, then the last visit date when investigational product was returned will be used in the calculation of investigational product exposure.

19.6 Missing Date Information for Prior or Concomitant Medications

For prior or concomitant medications, incomplete (i.e., partially missing) start date and/or stop date will be imputed. When the start date and the stop date are both incomplete for a subject, impute the start date first.

19.6.1 Incomplete Start Date

The following rules will be applied to impute the missing numerical fields. If the stop date is complete and the imputed start date is after the stop date, then the start date will be imputed using the stop date.

Missing day and month

- If the year of the incomplete start date is the same as the year of the date of the first dose of double-blind investigational product, then the day and month of the date of the first dose of double-blind investigational product will be assigned to the missing fields.
- If the year of the incomplete start date is before the year of the date of the first dose of double-blind investigational product, then 31 December will be assigned to the missing fields.
- If the year of the incomplete start date is after the year of the date of the first dose of double-blind investigational product, then 01 January will be assigned to the missing fields.

Missing month only

• The day will be treated as missing and both month and day will be replaced according to the above procedure.

Missing day only

- If the month and year of the incomplete start date are the same as the month and year of the date of the first dose of double-blind investigational product, then the day of the date of the first dose of double-blind investigational product will be assigned to the missing day.
- If either the year is before the year of the date of the first dose of double-blind investigational product or if both years are the same but the month is before the month of the date of the first dose of double-blind investigational product, then the last day of the month will be assigned to the missing day.
- If either the year is after the year of the date of the first dose of double-blind investigational product or if both years are the same but the month is after the month of the date of the first dose of double-blind investigational product, then the first day of the month will be assigned to the missing day.

19.6.2 Incomplete Stop Date

The following rules will be applied to impute the missing numerical fields. If the date of the last dose of double-blind investigational product is missing, then replace it with the last visit date. If the imputed stop date is before the start date (imputed or non-imputed start date), then the imputed stop date will be equal to the start date.

Missing day and month

- If the year of the incomplete stop date is the same as the year as of the date of the last dose of double-blind investigational product, then the day and month of the date of the last dose of double-blind investigational product will be assigned to the missing fields.
- If the year of the incomplete stop date is before the year of the date of the last dose of double-blind investigational product, then 31 December will be assigned to the missing fields.
- If the year of the incomplete stop date is after the year of the date of the last dose of double-blind investigational product, then 01 January will be assigned to the missing fields.

Missing month only

• The day will be treated as missing and both month and day will be replaced according to the above procedure.

Missing day only

- If the month and year of the incomplete stop date are the same as the month and year of the date of the last dose of double-blind investigational product, then the day of the date of the last dose of double-blind investigational product will be assigned to the missing day.
- If either the year is before the year of the date of the last dose of double-blind investigational product or if both years are the same but the month is before the month of the date of the last

dose of double-blind investigational product, then the last day of the month will be assigned to the missing day.

• If either the year is after the year of the last dose of double-blind investigational product or if both years are the same but the month is after the month of the date of the last dose of double-blind investigational product, then the first day of the month will be assigned to the missing day.

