10. PRIOR AND CONCOMITANT MEDICATION

Version WHODRUG March 2017 of the WHO drug dictionary will be used to classify prior and concomitant medications by preferred term.

Prior medication is defined as any medication taken prior to the date of first dose of investigational product.

Concomitant medication is defined as any medication with a start date prior to the date of the first dose of investigational product and continuing after the first dose of investigational product or with a start date between the dates of the first dose and last dose of investigational product, inclusive.

Any medication with a start date after the date of the last dose of investigational product (post-treatment) will not be considered a concomitant medication.

Both prior and concomitant medication usage will be summarized separately by the number and percentage of subjects receiving each medication within each preferred term by treatment group (SHP465 6.25 mg and Placebo) and overall for the Safety Set. Medications can be counted both as prior and concomitant medication. Multiple medication usage by a subject in the same category will be counted only once for the purpose of the summaries.

For ADHD medication history collected at the Screening Visit (Visit 1), version WHODRUG March 2017 of the World Health Organization (WHO) drug dictionary will be used to classify ADHD medications by preferred term. ADHD medication history will be summarized separately by the number and percentage of subjects receiving each medication within each preferred term by treatment group (SHP465 6.25 mg and Placebo) for the Safety Set. ADHD medication history will be listed for the Safety Set.

All prior, concomitant and post-treatment medications will be listed for the Safety Set.

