- Summary of duration of TEAE while on study drug: The duration of each event is the number of days from the onset of the TEAE, while on study drug during SHP465 6.25 mg, until the earlier of the end date of the TEAE or the date of last dosing + 3 days (if the date of last dosing is missing, the date of last day on study will be used). TEAEs that either overlap in time, or are adjacent in time will be merged into one TEAE only for the purposes of calculating duration of event. If a subject has multiple TEAEs that

Protocol SHP465-309

are not overlapping or adjacent in time, the durations will be averaged for that subject. Summary statistics are then based on the averaged subject durations. The calculated duration only includes the duration of TEAEs.

- Number and percentage of mild, moderate and severe TEAEs: Overlapping TEAEs with different preferred terms are counted as multiple TEAEs.
- Summary of the number of TEAEs per subject: Overlapping TEAEs with different preferred terms are counted as multiple TEAEs.
- Number and percentage of TEAEs that:
 - Resolved while on study drug
 - Ongoing
 - Dose interrupted
 - Dose withdrawn (and other action categories related to dose)
 - TEAEs leading to discontinuation
 - Number of subjects who discontinued investigational product due to the event

Also, for each of these 3 AEs, the following information will be presented by week:

- Number of subjects in the study
- Number and percentage of subjects with the TEAE
- Number of TEAEs
- Number and percentage of subjects who discontinued due to the TEAE
- Number and percentage of mild, moderate and severe TEAEs. If a subject has more than one TEAE in the same week, then the worst severity is counted.

Where, Week 1 includes TEAEs that start after Visit 2 (Baseline) through Visit 3 (Week 1), Week 2 includes TEAEs that start after Visit 3 (Week 1) through to Visit 4 (Week 2), Week 3 includes TEAEs that start after Visit 4 (Week 2) through to Visit 5 (Week 3), and Week 4 includes TEAEs that start after Visit 5 (Week 3) through to Visit 6 (Week 4).

In addition, for each subject, all occurrences of each of these 3 AEs will be listed separately by treatment group, subject, start date and stop date. The information presented will include: subject, sex, age, race, ethnicity, preferred term/adverse event, start date, stop date, onset day, study visit, last dose date, duration/imputed duration of TEAE (days), SAE, severity, effect on dosing and treatment for AE.

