19.7 Missing Date Information for Adverse Events

For AEs, incomplete (i.e., partially missing) start dates will be imputed and will follow the same rules as in Section 19.6.1. Incomplete stop dates will not be imputed.

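### A medicine recorded as stopped before first dose can be counted as concomitant, because SAP 19.6.1 checks an imputed start date only against a complete stop date

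*SAP*

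**What the plan says.** SAP 19.6 sets the order for medicines: "When the start date and the stop date are both incomplete for a subject, impute the start date first".

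SAP 19.6.1 imputes the start. If the day and month are missing and the year is that of first dose, "then the day and month of the date of the first dose of double-blind investigational product will be assigned to the missing fields". A start with only the month missing is treated the same way. The section has one check against the stop date, and it is conditional: "If the stop date is complete and the imputed start date is after the stop date", the start takes the stop date.

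SAP 19.6.2 imputes the stop. If only the day is missing and the month is before that of last dose, "then the last day of the month will be assigned to the missing day". If the result falls before the start, imputed or not, "then the imputed stop date will be equal to the start date".

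SAP 19.7 applies the start rules of 19.6.1 to adverse events. For their stop dates it says: "Incomplete stop dates will not be imputed".

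SAP 10 counts as concomitant a medicine that starts on any day from first to last dose, both days included. On the other class it says: "Prior medication is defined as any medication taken prior to the date of first dose of investigational product".

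**The concern.** Moving an unknown onset to the first-dose day is a common cautious convention when the timing really is unknown. Here it is not unknown: a stop month earlier than the first-dose month shows that the medicine ended before dosing. SAP 19.6.1 accepts this reasoning for a complete stop date, which overrides the imputed start. A partial stop date can be just as decisive, but the check does not cover it. SAP 19.6.2 then resolves the conflict the wrong way round, so that a guessed start overwrites a recorded stop month.

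At stake is the accuracy of the descriptive concomitant-medication table and, less often, of the adverse event tables. Partial dates before dosing are foreseeable. Protocol 5 asks for treatments from the 30 days before screening (or five half-lives, if longer) and for lifetime psychoactive medication history, and Protocol Table 2 requires washouts of 7 to 30 days.

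**Working it through.** The plan gives no figure on this point, so there is none to reproduce. The check applies the rules literally. All dates are illustrative assumptions: first dose 15 March 2018, last dose 11 April 2018 (first dose + 27 days).

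**One medicine: start recorded as 2018, stop recorded as February 2018**

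1. Start (19.6.1): the year equals the first-dose year and the month is missing, so the start becomes 15 March 2018.
2. Check against the stop (19.6.1): the stop date is not complete, so the check is skipped.
3. Stop (19.6.2): February is before April, the month of last dose, so the stop becomes 28 February 2018.
4. Conflict (19.6.2): 28 February is before 15 March, so the stop becomes 15 March 2018.
5. Class (SAP 10): the start lies within 15 March to 11 April inclusive, so the medicine is concomitant.

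**Neighbouring records, same first and last dose**

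| Start recorded | Stop recorded | Start used | Stop used | Class |
|---|---|---|---|---|
| 2018 | Feb 2018 | 15 Mar 2018 | 15 Mar 2018 | concomitant (wrong) |
| 2018 | 10 Feb 2018 | 10 Feb 2018 | 10 Feb 2018 | prior |
| Feb 2018 | Feb 2018 | 28 Feb 2018 | 28 Feb 2018 | prior |
| 3 Feb 2018 | Feb 2018 | 3 Feb 2018 | 28 Feb 2018 | prior |
| 2017 | Oct 2017 | 31 Dec 2017 | 31 Dec 2017 | prior |

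The first two rows differ only in whether the stop day is known. In the last row the recorded stop month is also overwritten, but the class stays right because 31 December 2017 is before dosing. The error is not tied to 2018: first dose 15 November 2017, start 2017 and stop October 2017 give 15 November 2017 for both dates. It cannot arise with a January first dose, because that year has no earlier month.

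**How wide the gap is**

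The rules were run over a grid of true start and stop dates, every third day from 1 June 2017 to mid-March 2018, with each date complete, day-missing or year-only (3 × 3 = 9 combinations). Only records whose known stop fields prove a stop before 15 March 2018 were kept: 3 × (4,656 + 4,186 + 2,628) = 34,410.

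- Year-only start with day-missing stop: 190 of 4,186 misclassified.
- The other eight combinations: 0.

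The 190 are all the records of the pattern above. The grid holds 19 dates in January and February 2018, giving 19 × 20 / 2 = 190 pairs with start not after stop. The other 3,996 records in that combination start in 2017 and get 31 December 2017. These counts show which records fail. They do not estimate how often such records occur in the trial.

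**After the fix**

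The latest date compatible with a stop of February 2018 is 28 February 2018. The start is capped there, the stop is imputed to the same day, and the medicine is prior only. Misclassified records in the grid fall from 190 to 0.

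**Adverse events**

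Only steps 1 and 2 apply. The onset becomes 15 March 2018, and the February end month is never compared with it, because 19.7 leaves partial stop dates as they are.

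**Size of one record**

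About 60 subjects randomized 1:1 gives about 30 per arm, and 1 / 30 = 3.3 percentage points in one row of one arm's table.

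**The case against.** The strongest case against is that this is a rare corner of a descriptive convention. It needs a start with unknown month in the first-dose year, together with a stop whose month is known, whose day is missing and which falls in an earlier month of that year. The documents give no count of such records, and Protocol 9.2 provides for queries on doubtful data. A medicine stopped on the site's instruction for washout is the kind most likely to have a full date. All of this stands and limits the weight of the point. It does not make the rule right, since no other section corrects the result.

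A reader might infer more than the documents support:

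- **That partial stop dates are ignored generally.** They are not. Eight of the nine date combinations are classified correctly.
- **That a pre-dose adverse event necessarily becomes treatment-emergent.** SAP 12.1 first requires the event to fall within the treatment period. A programmer could use that to exclude an event whose end month is before dosing. The route is also rare: events are collected only from consent, and screening is planned for up to 32 days.
- **That durations of insomnia, decreased appetite and weight decrease run too long.** SAP 12.1.1 counts "until the earlier of the end date of the TEAE or the date of last dosing + 3 days", and 19.7 leaves partial stop dates unimputed. Neither says how a partial end date enters the calculation. A missing duration fits the text as well as a long one.
- **That the medicine drops out of the prior table.** SAP 10 defines prior by when a medicine was taken, without mention of imputed dates, and lets a medicine count as both. Only the false concomitant status is certain.
- **That a washed-out stimulant would be reported as prohibited use.** SAP 7 has deviations recorded separately from the clinical database and reviewed by the study team. No section derives prohibited use from imputed dates.

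**Conclusion.** Wrong as written, minor. For this one date pattern the stated rules turn a medicine known to have ended before dosing into a concomitant one. That follows from the literal text of SAP 19.6, 19.6.1, 19.6.2 and 10 and needs no assumption beyond the record having those dates. The adverse event consequence is possible but not established. It comes from 19.6.1 with 19.7; the override in 19.6.2 governs medicines only. The 3.3-point figure is the effect of a single hypothetical record, not an expected bias. The primary and key secondary analyses do not use these dates.

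**What to change.** In SAP 19.6.1, replace the check that applies only to complete stop dates with: *if the imputed start date is later than the latest date compatible with the recorded stop date (the date itself, or the last day of its known month or year), set the start date to that latest date.* In SAP 19.7, state that this check also applies to adverse events, using the known fields of a partial stop date even though that date is not itself imputed.

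Leave the override in 19.6.2 unchanged. Restricting it to complete start dates may look like a natural companion edit, but it would create a new error. Take last dose 27 April 2018, start recorded as May 2018 and stop recorded as 2018. The start becomes 1 May 2018, and the new check allows this because the latest possible stop is 31 December 2018. The stop is imputed to 27 April 2018, before the start. The present override repairs this to 1 May; the restricted one would not.

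The cost is one replaced sentence, one added sentence and a small change to the date-imputation program. No new data are needed.
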